2.2 Research Group Experience

In a prospective 4-year study with a total of 90 patients²², the immediate post-operative and long-term course of patients undergoing DG-HAL hemorrhoid artery ligation was investigated. Totally, 64.4% of the included patients was discharged from the hospital, within 24 hours of the operation, 4.4% of patients needed additional analgesic treatment in the next 24 hours, while only 6.6% developed disease recurrence, one year after the operation. Additionally, a prospective randomized study of our clinic, compared pudendal nerve block and local anesthesia in 120 patients who underwent ultrasound scissors hemorrhoidectomy. A statistically significant lower rate of additional postoperative analgesic treatment was observed in the pudendal nerve block, while the level of postoperative pain, calculated on the Visual Analogue Scale (VAS scale), on the operative day was higher in the group of local anesthesia (5.1 vs. 2.2 $p < 0.001$)²³.

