3.2 Secondary endpoints

The secondary endpoints of the present study are:

- Operative time. Measurement unit: minutes. Time Frame: Intraoperative period
- Postoperative mobilization time. Measurement unit: hours. Time Frame: Postoperative period up to hospital discharge. Maximum time frame 24 hours
- Postoperative pain level at 12 hours after surgery, quantified with the use of the VAS scale. Time Frame: 12 hours postoperatively
- Onset of oral feeding. Measurement unit: hours. Time Frame: Postoperative period up to hospital discharge. Maximum time frame 24 hours
- Difference in the rates of adverse effects during hospitalization:
 - Hypotension. Occurrence of postoperative hypotension. If such an episode occurs, then it will be defined as=1 'YES' If such an episode does not occur, then it will be defined as=0 'NO'. Time Frame: Postoperative period up to hospital discharge. Maximum time frame 24 hours
 - Nausea. Occurrence of postoperative nausea. If such an episode occurs, then it will be defined as=1 'YES' If such an episode does not occur, then it will be defined as=0 'NO'. Time Frame: Postoperative period up to hospital discharge. Maximum time frame 24 hours
 - Vomiting. Occurrence of postoperative vomiting. If such an episode occurs, then it will be defined as=1 'YES' If such an episode does not occur, then it will be defined as=0 'NO'. Time Frame: Postoperative period up to hospital discharge. Maximum time frame 24 hours
 - Headache. Occurrence of postoperative headache. If such an episode occurs, then it will be defined as=1 'YES' If such an episode does not occur, then it will be defined as=0 'NO'. Time Frame: Postoperative period up to hospital discharge. Maximum time frame 24 hours
 - Urinary retention. Occurrence of postoperative urinary retention. If such an episode occurs, then it will be defined as=1 'YES' If such an episode does not occur, then it will be defined

- as=0 'NO'. Time Frame: Postoperative period up to hospital discharge. Maximum time frame 24 hours
- Bleeding at the operative site. Occurrence of postoperative bleeding at the operative site. If such an episode occurs, then it will be defined as=1 'YES' If such an episode does not occur, then it will be defined as=0 'NO'. Time Frame: Postoperative period up to hospital discharge. Maximum time frame 24 hours

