 - Constipation. Occurrence of postoperative constipation. If such an episode occurs, then it will be defined as=1 'YES' If such an episode does not occur, then it will be defined as=0 'NO'. Time Frame: 1 year postoperatively
 - Tenesmus. Occurrence of tenesmus. If such an episode occurs, then it will be defined as=1 'YES' If such an episode does not occur, then it will be defined as=0 'NO'. Time Frame: 1 year postoperatively.
 - Reoperation. Occurrence of reoperation. If the patient is reoperated, then it will be defined as=1 'YES' If the patient is not reoperated, then it will be defined as=0 'NO'. Time Frame: 1 year postoperatively
- Disease recurrence rate at 1 year postoperatively. Disease recurrence rate If such an episode occurs, then it will be defined as=1 'YES' If such an episode does not occur, then it will be defined as=0 'NO'. Time Frame: 1 year postoperatively
- Satisfaction level at 1 year postoperatively. Satisfaction level measured at a 0-10 scale. Time Frame: 1 year postoperatively
- Difference in the quality of life of the patient, at 1 month and 1 year postoperatively, compared to the respective preoperative measurements, based on the SF-36 questionnaire, weighted for the Greek. Time Frame: Preoperatively, 1 month postoperatively and 1 year postoperatively.

4. Analysis Set

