5.3 Statistical Procedures

The statistical estimations of this study will be based on a per protocol analysis. Prior to any computation, all data will be submitted to a Shapiro-Wilk normality test.

Continuous variables will be compared on the basis of an independent samples t-test, whereas for categorical variables, the Pearson chi-square test will be applied.

The effect of the various patient characteristics on the primary and secondary endpoint will be evaluated by a regression analysis. More specifically, a multiple linear and a logistic regression will be used for continuous and categorical variables, respectively.

Regression analysis will be applied to all distinct endpoints. The validity of the linear regression model will be confirmed by the assessment of the following assumptions:

- Independence of observations, assessed by the Durbin-Watson test
- Linear relationship between the dependent variable and each of the independent variables and between the dependent variable and all the independent variables, collectively.
- Homoscedasticity of the data
- Multicollinearity of the data
- Absence of significant outliers, high leverage points or highly influential points
- Normal distribution of the residuals

A Forward model will be introduced in our multiple linear regression analysis. The proportion of variance explained by our model will be represented by R square. The statistical significance of our model will be evaluated by the F-test. The effect of each independent variable on the dependent outcome will be provided by the respective coefficient and the 95%CI.

Similarly, a Forward model will be applied in our logistic regression analysis. The following assumption will be tested:

- Independence of observations and mutual exclusive and exhaustive categories
- Linear relationship between any continuous independent variable and the logit transformation of the dependent variable

The explained variance will be presented by the Cox & Snell R square and Nagelkerke R square test. The percentage of the correctly classified observations will be also estimated. The statistical significance of each variable will be calculated by the Wald test. The odds ratios of each variable will be also estimated, alongside the respective 95%CI.

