The variations between the different time endpoints SF-36 measurements will be evaluated on the basis of a repeated measures ANOVA model. Violation of the sphericity assumption will be determined by the Mauchly's test of Sphericity. In case of significant results, a Greenhouse-Geisser correction will be applied. Post-hoc comparisons will be performed with the introduction of Bonferroni corrections. The effect of the allocation group on the measured group will be quantified by the use of the F-test.

Continuous data will be reported as Mean (Standard Deviation), while categorical data will be reported as N (Percentage). Statistical significance will be considered at the level of p value < 0.05. All analyses will be performed in the IBM SPSS Statistics v23 software

4.LITERATURE

2. Chan A-W, Tetzlaff JM, Altman DG, et al. SPIRIT 2013 statement: defining standard protocol items for clinical trials. *Ann Intern Med* 2013;158:200–7.
3. Henderson AR. Testing experimental data for univariate normality. *Clin Chim Acta* 2006;366:112–129.

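### The SAP judges 26 secondary endpoints against one unadjusted p < 0.05 threshold, with no ordering, no exploratory label and no assured between-arm interval

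*SAP*

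**What the plan says.** SAP 3.2 opens with "The secondary endpoints of the present study are" and then gives a flat list, with none singled out as key. SAP 5.3 assigns the tests: "Continuous variables will be compared on the basis of an independent samples t-test, whereas for categorical variables, the Pearson chi-square test will be applied". SF-36 goes to a repeated-measures ANOVA. The decision rule is common to all analyses: "Statistical significance will be considered at the level of p value < 0.05".

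The only multiplicity provision is "Post-hoc comparisons will be performed with the introduction of Bonferroni corrections". It stands in the SF-36 paragraph and does not reach across endpoints.

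On intervals, SAP 5.3 states "Regression analysis will be applied to all distinct endpoints" and, for the linear models, "The effect of each independent variable on the dependent outcome will be provided by the respective coefficient and the 95%CI". The logistic models give odds ratios with 95% intervals in the same way. However, the section introduces the regressions as a study of patient characteristics and builds them by forward selection. SAP 4.6 lists demographics, symptoms and hemorrhoid grade as covariates, but not allocation group. Descriptive reporting is limited to mean with SD, or count with percentage.

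**The concern.** Two things are at stake.

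- **False positives.** With this many tests, one threshold and no stated status for the results, a chance finding would carry the same label as a real one. Operative time, pain, mobilization and discharge time are all on the list, and a reader would naturally look there for any practical advantage of one technique.
- **Uninformative non-significance.** Several listed outcomes may be uncommon. For these, 30 patients per arm give the test little power, and a p-value above 0.05 does not show how large a difference remains possible. An interval does, and the plan does not guarantee one for the comparison between arms.

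**Working it through.** **Count (SAP 3.2).** The 9 continuous or score endpoints are operative time, mobilization time, 12-hour pain, onset of feeding, time to safe discharge, 7-day pain, return to work, satisfaction and SF-36. The 17 binary endpoints are 6 in-hospital adverse effects, 4 complications at 7 days, 6 events at 1 year including reoperation, and recurrence. The total is 9 + 17 = 26.

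**The plan's own figure.** The documents give no family-wise error rate. The group size used below comes from SAP 5.1. Reading its 80% as power:

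n = (1.960 + 0.842)² × (0.725×0.275 + 0.90×0.10) / (0.175 + 0.10)² = 30.03 per arm, against the 30 stated.

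**Simple bound.** For 26 independent tests, each with true size 5% and every null true: 1 − 0.95²⁶ = 73.6%, and 26 × 0.05 = 1.3 false positives expected.

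**Allowing for the actual test.** Pearson chi-square at 30 per arm does not have size 5% when events are rare. Its true size s was found by summing the binomial probabilities of all tables (0–30 events in each arm) that give p < 0.05. With 9 full-size tests and 17 of size s:

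P(at least one) = 1 − 0.95⁹ × (1 − s)¹⁷; expected number = 9 × 0.05 + 17 × s.

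| Common binary event rate | s | P(at least one) | Expected |
|---|---|---|---|
| 1% | 0.03% | 37% | 0.46 |
| 2% | 0.3% | 40% | 0.50 |
| 3% | 1.0% | 47% | 0.62 |
| 5% | 2.8% | 61% | 0.93 |
| 6.6% | 4.1% | 69% | 1.15 |
| 10% | 5.4% | 76% | 1.37 |

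The 6.6% is the group's own recurrence figure (Protocol 2.2: "only 6.6% developed disease recurrence, one year after the operation"). The other rates, and the use of one rate for all binary endpoints, are assumptions.

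**Correlation.** In a simulation of 10,000 trials with an assumed common latent correlation of 0.5, P(at least one) is about 27%, 30%, 50% and 64% at rates of 1%, 2%, 5% and 10%. For given test sizes, correlation does not change the expected number.

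**What a p-value shows for a rare outcome.** Take 1-year recurrence near 6.6%, that is 2 events in 30 per arm. The Wilson limits for 2/30 (6.67%) are 1.85% and 21.32%. The Newcombe interval for the difference is 0 ± √[(6.67 − 1.85)² + (21.32 − 6.67)²] = ±15.4 points. The exact power of the chi-square test from 6.6% in one arm is:

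- 14.1% against 13.2% (a doubling)
- 68.7% against 30%
- 81.6% against 35%

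**Is an arm interval assured?** For treatment arm to receive a 95% interval under SAP 5.3, it would have to be entered in the regression and then survive forward selection. The plan states neither. The t-test and chi-square comparisons have no interval attached at all.

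**The case against.** The strongest reply is that the trial is sized on the primary endpoint alone. Unadjusted secondary tests in a 60-patient, single-centre study are then a matter of labelling, and the plan does provide 95% intervals for regression terms on every endpoint. Three stronger readings that a reader might infer do go too far.

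- **That a false positive is likely, at 73.6% with 1.3 expected.** This needs independent tests, every null true and every test at true size 5%. If most binary outcomes occur in 1–3% of patients, the chance is below 50%. The global null is also doubtful, since the arms differ in anesthesia (spinal against pudendal block; SAP 4.4 and 4.5).
- **That the plan has no between-arm interval.** The regression wording could be read to include arm. The text is ambiguous and does not exclude it.
- **That non-significant results will be reported as equality of the techniques.** Neither document says so. That would be a prediction about the report, not a feature of the plan.

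What survives: labelling is exactly what is missing, because nothing in the SAP calls these results exploratory. Even the lowest figure above, 27%, is more than five times 5%. An interval that depends on an unstated model term and a selection step is not a planned interval. Some nulls being false gives no error control for the others.

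**Conclusion.** The point holds in a limited form. One p < 0.05 rule governs 26 secondary endpoints with no ordering, no adjustment across endpoints and no exploratory label, and a between-arm interval is not assured for any of them. The false-positive chance of 37% to 76% rests on independence, all nulls true, 30 analysed per arm, a two-sided 5% threshold (the SAP does not state sidedness) and an assumed common event rate of 1% to 10%. The only in-house rate, 6.6%, gives 69%. Counting SF-36 once is conservative, because "Difference in the quality of life of the patient, at 1 month and 1 year postoperatively, compared to the respective preoperative measurements" already covers two time points.

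The interval half does not depend on those assumptions about the whole family of tests. With recurrence near the group's own rate, a comparison at 30 per arm leaves differences of about 15 points either way open, and a bare p-value would not show it. The primary analysis is unaffected. The issue is how most of the remaining results will be presented and how far they can be relied on.

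**What to change.** In SAP 5.3:

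1. For every secondary endpoint, report the between-arm difference with its 95% confidence interval: a risk difference for binary endpoints and a mean difference for continuous ones. For SF-36, give the between-arm difference in change from baseline at 1 month and at 1 year.
2. State that secondary p-values are unadjusted for multiplicity and exploratory.

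Naming a few key secondary endpoints with a multiplicity correction is optional and for the sponsor to choose. If they are to be tested only after success on the primary endpoint, SAP 5.3 must first define that success, since it describes no comparison with the 10% margin.

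The change is wording, with no extra patients or data. Its downside is that nominally significant secondary results can no longer be presented as confirmed.
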